## **10.7 Reporting to Novartis**

All SAEs should be reported, by FAX [REDACTED], to Novartis Pharmaceuticals Integrated Medical Safety Department within 24 hours of learning of its occurrence. This includes serious, related, labeled (expected) and serious, related, unlabeled (unexpected) adverse experiences. All deaths during treatment or within 30 days following completion of active protocol therapy must be reported within 1 working day.

## **10.8 Reporting to Hospital Risk Management**

Participating investigators will report to their local Risk Management office any subject safety reports or sentinel events that require reporting according to institutional policy.

## **10.9 Monitoring of Adverse Events and Period of Observation**

All adverse events, both serious and non-serious, and deaths that are encountered from initiation of study intervention, throughout the study, and within 30 days of the last study intervention should be followed to their resolution, or until the participating investigator assesses them as stable, or the participating investigator determines the event to be irreversible, or the participant is lost to follow-up. The presence and resolution of AEs and SAEs (with dates) should be documented on the appropriate case report form and recorded in the participant's medical record to facilitate source data verification.

For some SAEs, the study sponsor or designee may follow-up by telephone, fax, and/or monitoring visit to obtain additional case details deemed necessary to appropriately evaluate the SAE report (e.g., hospital discharge summary, consultant report, or autopsy report).

Participants should be instructed to report any serious post-study event(s) that might reasonably be related to participation in this study. Participating investigators should notify the DF/HCC Overall Principal Investigator and their respective IRB of any unanticipated death or adverse event occurring after a participant has discontinued or terminated study participation that may reasonably be related to the study.

## 11. DATA AND SAFETY MONITORING

### 11.1 Data Reporting

#### 11.1.1 Method

The QACT will collect, manage, and monitor data for this study. Electronic case report forms (eCRFs) will be used.

#### 11.1.2 Data Submission

**Table 8. Schedule for completion and submission of eCRFs to the QACT**

| Form                         | Submission Timeline  |
|------------------------------|--|
| Eligibility Checklist        | Complete prior to registration with QACT                                       |
| On Study Form                | Within 14 days of registration   |
| Baseline Assessment Form     | Within 14 days of registration   |
| Treatment Form               | Within 10 days of the last day of the cycle                                    |
| Adverse Event Report Form    | Within 10 days of the last day of the cycle                                    |
| Response Assessment Form     | Within 10 days of the completion of the cycle required for response evaluation |
| Off Treatment/Off Study Form | Within 14 days of completing treatment or being taken off study for any reason |
| Follow up/Survival Form      | Within 14 days of the protocol defined follow up visit date or call            |

## 11.2 Safety Meetings

The DF/HCC Data and Safety Monitoring Committee (DSMC) will review and monitor toxicity and accrual data from this trial. The committee is composed of clinical specialists with experience in oncology and who have no direct relationship with the study. Information that raises any questions about participant safety will be addressed with the Principal Investigator and study team.

The DSMC will meet quarterly and/or more often if required to review toxicity and accrual data. Information to be provided to the committee may include: up-to-date participant accrual; current dose level information; DLT information; all grade 2 or higher unexpected adverse events that have been reported; summary of all deaths occurring within 30 days for Phase I or II protocols; for gene transfer protocols, summary of all deaths while being treated and during active follow-up; any response information; audit results, and a summary provided by the study team. Other information (e.g. scans, laboratory values) will be provided upon request.

## 11.3 Monitoring

Involvement in this study as a participating investigator implies acceptance of potential audits or inspections, including source data verification, by representatives designated by the DF/HCC Overall Principal Investigator (or Protocol Chair) or DF/HCC. The purpose of these audits or inspections is to examine study-related activities and documents to determine whether these activities were conducted and data were recorded, analyzed, and accurately reported in accordance with the protocol, institutional policy, Good Clinical Practice (GCP), and any applicable regulatory requirements.

All data will be monitored for timeliness of submission, completeness, and adherence to protocol requirements. Monitoring will begin at the time of participant registration and will continue during protocol performance and completion.

# 12. REGULATORY CONSIDERATIONS

## 12.1 Protocol Review and Amendments

This protocol, the proposed informed consent and all forms of participant information related to the study (e.g., advertisements used to recruit participants) and any other necessary documents must be submitted, reviewed and approved by a properly constituted IRB governing each study location.

Any changes made to the protocol must be submitted as amendments and must be approved by the IRB and by Novartis prior to implementation. Any changes in study conduct must be reported to the IRB. The DF/HCC Overall Principal Investigator will disseminate protocol amendment information to all participating investigators.

All decisions of the IRB concerning the conduct of the study must be made in writing.

## 12.2 Informed Consent

All participants must be provided a consent form describing this study and providing sufficient information for participants to make an informed decision about their participation in this study. The formal consent of a participant, using the IRB approved consent form, must be obtained before the participant is involved in any study-related procedure. The consent form must be signed and dated by the participant or the participant's legally authorized representative, and by the person obtaining the consent. The participant must be given a copy of the signed and dated consent document. The original signed copy of the consent document must be retained in the medical record or research file.

## 12.3 Ethics and Good Clinical Practice (GCP)

This study is to be conducted according to the following considerations, which represent good and sound research practice:

- E6 Good Clinical Practice: Consolidated Guidance  
[www.fda.gov/downloads/RegulatoryInformation/Guidances/UCM129515.pdf](http://www.fda.gov/downloads/RegulatoryInformation/Guidances/UCM129515.pdf)
- US Code of Federal Regulations (CFR) governing clinical study conduct and ethical principles that have their origin in the Declaration of Helsinki
  - Title 21 Part 11 – Electronic Records; Electronic Signatures  
[www.access.gpo.gov/nara/cfr/waisidx\\_02/21cfr11\\_02.html](http://www.access.gpo.gov/nara/cfr/waisidx_02/21cfr11_02.html)
  - Title 21 Part 50 – Protection of Human Subjects  
[www.access.gpo.gov/nara/cfr/waisidx\\_02/21cfr50\\_02.html](http://www.access.gpo.gov/nara/cfr/waisidx_02/21cfr50_02.html)
  - Title 21 Part 54 – Financial Disclosure by Clinical Investigators  
[www.access.gpo.gov/nara/cfr/waisidx\\_02/21cfr54\\_02.html](http://www.access.gpo.gov/nara/cfr/waisidx_02/21cfr54_02.html)
  - Title 21 Part 56 – Institutional Review Boards  
[www.access.gpo.gov/nara/cfr/waisidx\\_02/21cfr56\\_02.html](http://www.access.gpo.gov/nara/cfr/waisidx_02/21cfr56_02.html)
  - Title 21 Part 312 – Investigational New Drug Application  
[www.access.gpo.gov/nara/cfr/waisidx\\_02/21cfr312\\_02.html](http://www.access.gpo.gov/nara/cfr/waisidx_02/21cfr312_02.html)
- State laws
- DF/HCC research policies and procedures  
<http://www.dfhcc.harvard.edu/clinical-research-support/clinical-research-unit-cru/policies-and-procedures/>

It is understood that deviations from the protocol should be avoided, except when necessary to eliminate an immediate hazard to a research participant. In such case, the deviation must be reported to the IRB according to the local reporting policy.

## 12.4 Study Documentation

The investigator must prepare and maintain adequate and accurate case histories designed to record all observations and other data pertinent to the study for each research participant. This information enables the study to be fully documented and the study data to be subsequently verified.

Original source documents supporting entries in the case report forms include but are not limited to hospital records, clinical charts, laboratory and pharmacy records, recorded data from automated instruments, microfiches, photographic negatives, microfilm or magnetic media, and/or x-rays.

## 12.5 Records Retention

All study-related documents must be retained for the maximum period required by applicable federal regulations and guidelines or institutional policies.

# 13. STATISTICAL CONSIDERATIONS

## 13.1 Study Design/Endpoints

The primary purpose of this study is to determine the efficacy of AUY922 when administered intravenously on a once-weekly schedule at 70 mg/m^2 in adult NSCLC patients with advanced disease and EGFR exon 20 insertion mutations. The design will be a Simon two-stage phase 2 study, with 10 patients enrolled to the first stage and an additional 19 patients enrolled to the second stage provided we observe at least 1 partial or complete response or stable disease lasting  $\geq 3$  months in the first stage.

The Primary Objective is:

- To evaluate the overall response rate to AUY922 in patients with advanced NSCLC and exon 20 insertion mutations in *EGFR*.

Secondary Objectives include:

- To estimate progression-free survival (PFS) and overall survival (OS) in the study population
- To determine the safety and tolerability of AUY922
- To explore variance in clinical outcome between different types of exon 20 EGFR mutations

## 13.2 Sample Size/Accrual Rate

A Simon two-stage design will be used. In this design we will consider a rate of response plus SD lasting  $\geq 3$  months that is no greater than 5% as evidence that AUY922 is ineffective as a monotherapy in patients with exon 20 insertion mutations in *EGFR*, and 20% will be the target rate of effectiveness. In other words,  $H_0=0.05$  and  $H_a=0.20$ .

This design requires that 10 patients will be initially enrolled (the first stage of the Simon design). If there are no responses or patients with SD lasting  $\geq$  3 months in these 10 patients then AUY922 will be considered ineffective in *EGFR* exon 20 insertion mutation patients. If at least 1 PR or SD lasting  $\geq$  3 months is noted, then an additional 19 patients will be enrolled (the second stage of the Simon design).

If the total number of responses plus SD lasting  $\geq$  3 months in the entire set of 29 patients is 4 or more, then AUY922 will be considered for further evaluation, likely in a randomized setting. If the number of responses of PR or SD lasting  $\geq$  3 months is 3 or fewer in the entire set of 29 patients, then AUY922 will be considered potentially ineffective and further investigation may be unwarranted.

Using this design, if AUY922 is actually not effective, there is a 0.047 probability of concluding that it is (the target for this value was 0.050, the  $\alpha$ -level). If the drug is actually effective, there is a 0.199 probability of concluding that it is not (the target for this value was 0.200, the beta-level [80% power]). The power and  $\alpha$ -level are slightly different from the nominal values due to the discrete nature of the binomial distribution of response.

Among the three participating clinics (MGH, DFCI and BIDMC), we expect to enroll approximately 1.5 patients per month. Therefore, assuming full enrollment to 29 patients, accrual should be complete within 20 months.

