## 1. OBJECTIVES

### 1.1 Study Design

The primary purpose of this study is to determine the efficacy of AUY922 when administered intravenously on a once-weekly schedule at 70 mg/m^2 in adult NSCLC patients with advanced disease and *EGFR* exon 20 insertion mutations. The design will be a Simon two-stage phase 2 study, with 10 patients enrolled to the first stage and an additional 19 patients enrolled to the second stage provided we observe at least 1 partial or complete response or stable disease lasting  $\geq$  3 months in the first stage. Additional safety and tolerability assessments of AUY922 will be evaluated as secondary objectives. Pre- and post-treatment biopsy specimens, if available, will also be analyzed to determine which exon 20 *EGFR* mutations may be most sensitive to Hsp90 inhibition and explore potential mechanisms of resistance to treatment.

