### 1.2 Primary Objectives

To evaluate the overall response rate to AUY922 in patients with advanced NSCLC and exon 20 insertion mutations in *EGFR*.

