### CAUY922A2206: A Phase 2 Study of AUY922 in NSCLC Patients

As of April 2012, 121 patients with NSCLC have been treated on this phase 2 study examining the activity of AUY922 in patients with defined molecular subtypes of NSCLC who had received prior chemotherapy. The molecular groups included were those with *EGFR* mutations, those with *KRAS* mutations, those with *EML4-ALK* rearrangements, and those that were wild-type for all 3 driver mutations. Patients were treated at 70mg/m^2 and the primary outcome was rate of partial response (PR) and prolonged stable disease (SD; >18 weeks) within each molecular subgroup. Interestingly, the *EGFR* mutant subgroup had a 20% response rate and the *ALK* rearranged group had a 29% response rate on this phase II study (Garon, 2012), supporting further study of AUY922 in both of these molecularly-defined patients groups.

The most frequent adverse events (AEs, all grades) were visual AEs (77%), diarrhea (74%), and nausea (46%). Overall 7% of patients had a grade 3 or 4 AE involving visual symptoms; most commonly photopsia (20%), visual impairment (19%), vision blurred (18%), night blindness (17%), and visual acuity reduced (17%). These effects were all reversible upon discontinuation of drug.

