### 9.1.3 Response Criteria

#### 9.1.3.1 Evaluation of Target Lesions

Complete Response (CR):

Disappearance of all target lesions. Any pathological lymph node must have reduction in short axis to  $< 10$  mm.

Partial Response (PR):

At least a 30% decrease in the sum of the diameters of target lesions, taking as reference the baseline sum diameters.

Progressive Disease (PD):

At least a 20% increase in the sum of the diameters of target lesions, taking as reference the smallest sum on study with at least a 5 mm absolute increase in the sum of all lesions. The appearance of one or more new lesions\* denotes disease progression.

Stable Disease (SD):

Neither sufficient shrinkage to qualify for PR nor sufficient increase to qualify for PD, taking as reference the smallest sum diameters while on study.

Unknown (UN): Assessment of target lesions cannot be made due to insufficient or unevaluable data. In this case, a concise explanation must be given.

**Note:** If tumor response data is missing for target lesions, the overall assessment must be UN unless there is new disease that would result in an overall assessment of PD. However, if there is missing or unevaluable data for non-target lesions, but data is available for all target lesions, the overall response for that time point will be assigned based on the sum LD of all target lesions. Additionally, the assessment of CR cannot be made if there is missing or unevaluable data for non-target lesions. In this case, the overall assessment would be PR.

**\*Definition of New Lesion:** The finding of a new lesion should be unequivocal (i.e. not due to difference in scanning technique, imaging modality, or findings thought to represent something other than tumor (ex: new bone lesions may be healing or flare of pre-existing lesions). However, a lesion identified on a follow-up scan in an anatomical location that was not scanned at baseline is considered new and will indicate PD. If a new lesion is equivocal (because of small size, etc.), follow-up evaluation will clarify if it truly represents new disease and if PD is confirmed, progression should be declared using the date of the initial scan on which the lesion was discovered.

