### **13.6 Analysis of Response Rate**

Response rate will be assessed as per RECIST, see Section 9.1. Results will be reported with 95% confidence intervals. All patients will be evaluable for response rate.

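### The primary objective and its analysis are overall response rate, but the Simon rules and error rates are set for response plus stable disease of at least 3 months, so a go is possible with no responses.

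*Combined protocol and SAP*

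**What the plan says.** The objective is stated the same way in Sections 1.2 and 13.1: "To evaluate the overall response rate to AUY922 in patients with advanced NSCLC and exon 20 insertion mutations in" *EGFR*. Section 13.6 gives the only planned analysis of tumour response: "Response rate will be assessed as per RECIST, see Section 9.1. Results will be reported with 95% confidence intervals".

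The decision rules use a different event. Under Sections 1.1 and 13.1 the second stage opens "provided we observe at least 1 partial or complete response or stable disease lasting" at least 3 months. Section 13.2 sets the null and target rates on that same composite ("In this design we will consider a rate of response plus SD lasting" at least 3 months), at 5% and 20%. It stops the trial if none of the first 10 patients qualifies and recommends further evaluation if 4 or more of 29 do. The operating characteristics follow: "Using this design, if AUY922 is actually not effective, there is a 0.047 probability of concluding that it is", with a type II error of 0.199.

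Section 9.1.3.1 defines SD as "Neither sufficient shrinkage to qualify for PR nor sufficient increase to qualify for PD". Table 7 lists CR, PR and SD as separate categories, and Section 9.1.4 starts the duration of response at CR or PR.

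**The concern.** SD is not a response under the protocol's own criteria, so the quantity that decides the trial is not the quantity called primary. The composite appears in no list of objectives and has no planned estimate or interval. ORR, which has both, has no hypothesis, cut-off or error rate.

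Two consequences follow. The trial can end with a positive recommendation beside a null primary result, and nothing in the plan says which governs. And 0.047 cannot be quoted as the false-positive risk for the primary objective. Even for the composite, it is the false-positive risk only if 5% is the right rate for an inactive drug once SD counts. The sections I had give no support for that figure. The text around Section 2.3 (Rationale) was not available to me and may contain some.

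**Working it through.** **Inputs (Section 13.2).** n1 = 10, stop if 0 qualify; n2 = 19; go if at least 4 of 29 qualify; p0 = 0.05; p1 = 0.20.

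**Reproducing the plan's figures.** With p the probability that a patient counts,

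P(go) = Σ over x = 1,…,10 of P[Bin(10, p) = x] × P[Bin(19, p) ≥ max(0, 4 − x)].

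| Stage 1 count | p = 0.05 | p = 0.20 |
|---|---|---|
| 1 | 0.3151 × 0.0665 = 0.0210 | 0.2684 × 0.7631 = 0.2048 |
| 2 | 0.0746 × 0.2453 = 0.0183 | 0.3020 × 0.9171 = 0.2770 |
| 3 | 0.0105 × 0.6226 = 0.0065 | 0.2013 × 0.9856 = 0.1984 |
| 4 or more | 0.0010 | 0.1209 |
| **P(go)** | **0.0468** | **0.8011** |

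So alpha is 0.0468 and beta is 1 − 0.8011 = 0.1989, matching 0.047 and 0.199. The arithmetic is right, for whatever event is counted. Section 13.2 counts response plus durable SD.

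**A go with no responses.** Four patients with SD of at least 3 months, at least one among the first 10, satisfy both rules with 0/29 responses. The exact 95% upper limit for ORR is then 1 − 0.025^(1/29) = 0.119.

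**Sensitivity to the 5% null.** Solving P(go) = 0.05, 0.10 and 0.20 gives p = 0.051, 0.065 and 0.085. The false-go risk doubles to 10% by a composite rate of 6.5%.

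**If an inactive drug produces no responses but some durable SD** (assumed rates; none is given in the sections reviewed). P(pass stage 1) = 1 − (1 − p)^10.

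| SD ≥ 3 months | P(pass stage 1) | P(go) |
|---|---|---|
| 5% | 0.401 | 0.047 |
| 10% | 0.651 | 0.289 |
| 15% | 0.803 | 0.589 |
| 20% | 0.893 | 0.801 |
| 25% | 0.944 | 0.913 |

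**If true ORR equals 5% and further patients have durable SD** (same caveat). P(go) uses p = ORR + SD rate. The other columns split the qualifying patients into responses and SD with a trinomial model.

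| Further SD ≥ 3 months | P(go) | P(go, fewer than 4 responses) | P(go, no responses) |
|---|---|---|---|
| 5% | 0.289 | 0.239 | 0.012 |
| 10% | 0.589 | 0.537 | 0.073 |
| 15% | 0.801 | 0.748 | 0.142 |

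With no durable SD at all, P(go) at ORR 5% is 0.047. The printed alpha describes ORR only in that case.

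**The case against.** The strongest reply is that counting SD was deliberate. The composite is used in Sections 1.1, 13.1 and 13.2, and Section 2.1.3 gives a precedent: in the earlier AUY922 study in NSCLC the "primary outcome was rate of partial response (PR) and prolonged stable disease" of more than 18 weeks. Section 13.2 openly attaches its error rates to the composite and never claims 0.047 for ORR. A go only leads to consideration for further study, and a plan may report one endpoint while gating on another.

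Much of this is fair. The composite may well be the intended endpoint. If so, Sections 1.2, 13.1 and 13.6 are the ones to correct. That settles where the correction goes, not whether one is needed. A plan may separate the gate from the reported endpoint, but it has to say so, and this one does not.

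A second reply is that the larger probabilities rest on assumed SD rates, and that a go with no responses at all is much less likely than a go with fewer than four. Both points stand, and the zero-response column is shown above for that reason. The mismatch itself depends on no assumed rate.

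**Conclusion.** The concern holds and must be fixed. From the documents alone, the primary objective and its analysis concern ORR, while both decision rules, both hypothesised rates and both error rates concern response plus SD of at least 3 months. That composite is not a listed endpoint and has no planned estimate. The calculations in Section 13.2 are correct for it.

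How far the go probability moves from 0.047 at a true ORR of 5% depends on the durable SD rate: between 29 and 80% for assumed rates of 5 to 15%. The statement that 5% is unsupported as a null for the composite is limited to the sections I could read.

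**What to change.** Make the primary endpoint and the decision rule the same, keeping 29 patients.

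- **Option (a), ORR decides.** In Sections 1.1, 13.1 and 13.2, count only CR and PR: continue with at least 1 of 10, go with at least 4 of 29. The figures 0.047 and 0.199 then hold for ORR 5% against 20%. Report response plus SD of at least 3 months as a secondary endpoint with a 95% CI.
- **Option (b), the composite decides.** Name it as primary in Sections 1.2, 13.1 and 13.6, report it with a 95% CI and keep ORR as secondary. Justify the null and target rates for an endpoint that includes SD, and recompute the cut-offs and error rates if those rates change. As illustration only, with no basis in the documents: 25% against 50%, continuing with at least 3 of 10 and a go with at least 12 of 29, gives alpha 0.036 and power 0.84.

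Under either option, use one list of qualifying outcomes throughout. Section 13.2 twice mentions PR or SD without CR.

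The cost is an amendment, which under Section 12.1 "must be approved by the IRB and by Novartis prior to implementation"; no extra patients or procedures are needed. Option (a) changes the decision for a drug that mainly stabilises disease: with ORR 10% and a further 15% with durable SD (illustrative rates), P(go) falls from 0.91 (p = 0.25) to 0.29 (p = 0.10). Option (b) keeps the counted event but needs a defensible null, and higher cut-offs if that null is above 5%.
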